5.2 Secondary endpoints

- Cumulative incidence of newly diagnosed HCC at Week 48, Week 96, Week 144, and Week 192.
- Cumulative incidence of disease progression at Week 48, Week 96, Week 144, and Week 192.
- The mean changes of liver stiffness measurement (LSM) at Week 12, Week 24, Week 36, Week 48, Week 96, Week 144, Week 192 and Week 240 for patients with baseline ALT > ULN,

baseline ALT \leq ULN and overall.

- Change of fibrosis stage for subjects with baseline ALT $>$ ULN and ALT \leq ULN.
- Change of non-invasive liver fibrosis evaluation index (GPR, APRI and FIB-4, defined in Section 8.5, appendix 5) from baseline by visit.
- The proportion of subjects with serum HBV DNA $<$ 20 IU/mL or serum HBV DNA $<$ 69 IU/mL (Roche COBAS Taqman HBV Test) at Week 12, Week 24, Week 36, Week 48, Week 96, Week 144, Week 192 and Week 240
- The mean \log_{10} IU/mL reduction in serum HBV DNA at Week 12, Week 24, Week 36, Week 48, Week 96, Week 144, Week 192 and Week 240 compared with baseline
- The proportion of subjects with ALT normalization at Week 48, Week 96, Week 144, Week 192 and Week 240 in subjects who have abnormal ALT at baseline
- For HBeAg positive subjects: the proportion of subjects achieving HBeAg loss, HBeAg seroconversion or HBsAg loss and HBsAg seroconversion at Week 24, Week 48, Week 96, Week 144, Week 192 and Week 240
- For HBeAg negative subjects: the proportion of subjects achieving HBsAg loss and HBsAg seroconversion at Week 48, Week 96, Week 144, Week 192 and Week 240
- Incidence of virological breakthrough as defined by 1 \log_{10} IU/mL increase in HBV DNA from nadir (as determined by two sequential HBV DNA measurements at least 1 month apart, or the last on-treatment measurement) overall and by each visit
- The proportion of subject with unsatisfactory response, overall and by each visit. Unsatisfactory response is defined as subjects who have HBV DNA \geq 200 IU/mL at week 48 and afterwards have \leq 1 \log_{10} IU/mL decrease in HBV DNA at two consecutive tests, confirmed by a third visit (additional visit) at least one month apart
- Subject safety as determined by adverse events and laboratory assessments

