6.2 Data handling

Missing data can have an impact upon the interpretation of the trial data. In general, values for missing data will not be imputed unless otherwise specified. For baseline value, if it is missing at baseline visit, then the latest non-missing value of screening will be used to replace.

All serum HBV DNA results below the lower limit of detection (<20 IU/mL) or results of “not detected” will be analyzed as being the value of the lower limit of quantification, which is 20 IU/mL. For patients whose week 240 visits were influenced by COVID-19, a safety follow-up were added for these subjects. The missing week 240 will be imputed from safety follow-up visit in the analysis of primary endpoints. Please refer to section 7.4 for details.

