7.4 Efficacy analysis

All analysis will be conducted in mITT, unless otherwise specified.

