7.4.3 Exploratory analysis

Incidence of TDF resistance substitutions such as mutation change, drug resistance test results will be summarized in patients with unsatisfied virological response, viral breakthrough, or discontinued treatment with HBV DNA ≥ 20 IU/mL.

Univariate and multivariate analysis by logistic regression model will be performed to identify baseline or on-treatment risk factors associated with HCC and disease progression, if applicable. The factors will include gender, age, genotype, baseline HBV DNA category (≥ 2000 or < 2000, IU/mL), baseline HBeAg sero-status, baseline ALT value, baseline LSM value, Week 24 treatment response, Week 48 treatment response. Treatment response is defined as serum HBV DNA < 20 IU/mL. Multivariate analysis will include sex, age and the factors with P ≤ 0.20 in univariate analysis.

Time to HCC/disease progression will be analyzed by cox model. Univariate will be conducted to include all above factors and the selection of multivariate analysis will follow the same rule.

Impact of HBV DNA and virologic response on change of LSM will be summarized by shift table

of descriptive statistics as the mean, standard deviation, minimum, median, maximum, and the number of observations.

The mean changes and percent of the changes of liver stiffness measurement in each visit will be summarized by descriptive statistics as the mean, standard deviation, minimum, median, maximum, and the number of observations for patients with advanced fibrosis and compensated cirrhosis. Compensated cirrhosis is defined as $LSM \geq 12.0$ Kpa ($ALT \leq ULN$) or $LSM \geq 17.5$ Kpa ($ALT > ULN$); advanced fibrosis is defined as 9.0 Kpa $\leq LSM < 12.0$ Kpa ($ALT \leq ULN$) or 12.4 Kpa $\leq LSM < 17.5$ Kpa ($ALT > ULN$).

Time to improvement of fibrosis will be analyzed by cox regression. Improvement of fibrosis is defined as at least 30% decrease of LSM compared with baseline. Univariate analysis will include gender, age, genotype, baseline HBV DNA category (≥ 2000 or < 2000 , IU/mL), baseline HBeAg sero-status, baseline ALT value, Week 24 treatment response, Week 48 treatment response. Treatment response is defined as serum HBV DNA < 20 IU/mL. Multivariate analysis will include sex, age and the factors with $P \leq 0.20$ in univariate analysis.

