The relationship between baseline variables or on-treatment variables and improvement of fibrosis will be analysis by univariate and multivariate logistic model. Univariate analysis will include gender, age, BMI category (< 25 or ≥ 25 kg/m²), baseline HBV DNA (≥ 2000 or < 2000 , IU/mL), baseline HBeAg sero-status, baseline ALT value, baseline LSM value, baseline total bilirubin, HBeAg loss at Week 24, treatment response at Week 24 and Week 48, ALT normalized or not at Week 24 and Week 48, change from baseline of LSM at Week 12 and Week 24, change from baseline of GGT at Week 24. Multivariate analysis will include sex, age and the factors with $P \leq 0.20$ in univariate analysis.

Proportion of LSM improvement will be summarized at Week48, Week96, Week144, Week192 and Week240 for patients with baseline LSM result in following groups: LSM improved (LSM decreased from baseline $\geq 30\%$), LSM stable (LSM decreased from baseline $< 30\%$ or no change from baseline), and LSM deteriorate (LSM increase from baseline).

Proportion of fibrosis stage improvement will be summarized at Week 48, Week 96, Week 144, Week 192 and Week 240 for patients of fibrosis stage measured by fibrosis improved from baseline, ≥ 2 stage fibrosis stage improved from baseline, ≥ 1 stage fibrosis stage, no change from baseline, fibrosis stage increase from baseline.

Analyses of correlation coefficients between LSM and ALT level will be analyzed by Pearson correlation coefficients and P-value during every 48 weeks by patients with ALT normal at baseline, patients with abnormal at baseline and overall.

Correlation coefficients between variables change at Week 12 and 24 and LSM change at Week 240 will be analyzed by correlation coefficients and P-value. The change from baseline of Gamma-Glutamyltransferase (GGT), Total Bilirubin (TBIL), Albumin (ALB), International Normalized Ratio (INR) and LSM will be included in the analysis of correlation coefficients at Week 12, platelets (PLT), GPR, APRI, FIB-4 and all the variables included at Week 12 will be included in the analysis of correlation coefficients at Week 24.

A 5-years predicted HCC risks by REACH-B model (see Section 8.5) and observed HCC risks (cumulative incidence of HCC) at Week 240 will be presented in table. Decline in LSM from baseline to Week 240 by visit will be analyzed by a line plot.

In addition, a listing of HBV DNA result will be provided for the following patients:

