Table	4.7.3	The Proportion of Subjects Achieving HBsAg Loss and HBsAg Seroconversion at Week 48, 96, 144, 192 and 240 for Subjects with Negative HBeAg at Baseline - mITT
Table	4.8.1	Change from Baseline for the log ₁₀ IU/mL in Serum HBV DNA by Visit - mITT
Table	4.9.1	Incidence of Subjects Who Experience Viral Breakthrough by Visit - mITT
Table	4.9.3	Incidence of Subjects With Unsatisfied Response by Visit - mITT
Table	4.10.1	The Proportion of Subjects with Histological Improvement - mITT
Table	4.11.1	The Proportion of Subjects with Cirrhosis Reversal - mITT

Table	4.12.1	The Mean Changes of Liver Stiffness Measurement by Visit - mITT
Table	4.12.3.1.1	Shift from Baseline in Fibrosis Stage for Patients with Baseline ALT > ULN - mITT
Table	4.12.3.2.1	Shift from Baseline in Fibrosis Stage for Patients with Baseline ALT ≤ ULN - mITT
Table	4.12.3.3	Shift from Baseline in Fibrosis Stage - mITT
Table	4.13.1	Incidence of TDF Resistance Substitutions - mITT
Table	4.14.1	The Relationship Between Baseline Variables or On-treatment Variables and Newly Diagnosed Hepatocellular Carcinoma (HCC) - mITT
Table	4.14.3	The Relationship Between Baseline Variables or On-treatment Variables and Disease Progression - mITT
Table	4.17.1	Cox Regression Analysis for Time to Newly Diagnosed Hepatocellular Carcinoma (HCC) - mITT
Table	4.17.3	Cox Regression Analysis for Time to Disease Progression - mITT
Table	4.18.1	Impact of HBV DNA and Virologic Response on Change of LSM - mITT
Table	4.18.3	The Mean Changes of Liver Stiffness Measurement by Visit for Patients with Advanced Fibrosis and Compensated Cirrhosis - mITT
Table	4.18.3.1	The % Changes of Liver Stiffness from baseline by Visit for Patients with Advanced Fibrosis and Compensated Cirrhosis - mITT
Table	4.19.7	Cox Regression Analysis for Time to Improvement of Fibrosis - mITT
Table	4.20.3	The Relationship Between Baseline Variables or On-treatment Variables and Improvement of Fibrosis - mITT
Table	4.21.1	Proportion of LSM Improvement - mITT
Table	4.21.3	Proportion of LSM Stage Improvement - mITT
Table	4.22.1	Analyses of correlation coefficients between LSM and ALT level - mITT
Table	4.23.1	Analyses of correlation coefficients between Variables Change at Week 12 and 24 and LSM Change at Week240 - mITT
Table	4.24.1	Predicted and Observed Risk of HCC at Week240 - mITT
Table	5.3.4	Mean values in Non-invasive fibrosis - SA
Table	5.1.1	Overall Summary of Adverse Events - SA

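### The fibrosis-improvement logistic model uses ALT normalization and HBeAg loss across mITT without saying how subjects who cannot have these events are handled; yes/no coding can confound them with baseline group, and blank coding shrinks the multivariable model.

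*SAP*

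**What the plan says.** SAP 7.4.3 plans univariate and multivariate logistic models relating baseline and on-treatment variables to improvement of fibrosis. The outcome is given in the same section: "Improvement of fibrosis is defined as at least 30% decrease of LSM compared with baseline". The candidates include "HBeAg loss at Week 24, treatment response at Week 24 and Week 48, ALT normalized or not at Week 24 and Week 48", together with baseline HBeAg serostatus and baseline ALT value. Selection is by univariate screen: "Multivariate analysis will include sex, age and the factors with" a univariate P of at most 0.20.

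The population is set by SAP 7.4: "All analysis will be conducted in mITT, unless otherwise specified". Nothing else is specified for this model, and Table 4.20.3 in SAP 9 is titled "The Relationship Between Baseline Variables or On-treatment Variables and Improvement of Fibrosis - mITT".

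Elsewhere the SAP gives both events a restricted denominator. SAP 5.2 has "ALT normalization at Week 48, Week 96, Week 144, Week 192 and Week 240 in subjects who have abnormal ALT at baseline" and "For HBeAg positive subjects: the proportion of subjects achieving HBeAg loss"; SAP 7.4.2.3 keeps the same restrictions and carries two ALT definitions, the lab report and the AASLD criteria. Inclusion criterion 3 (protocol 4.2, SAP 8.1) admits HBeAg-negative subjects, and subjects with or without raised ALT. On missing values SAP 6.2 says: "In general, values for missing data will not be imputed unless otherwise specified".

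**The concern.** A subject with normal ALT at baseline cannot normalize, and an HBeAg-negative subject cannot lose HBeAg. Both kinds of subject may be in mITT, and the SAP does not say what value they take. There are three options:

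- **Coded as no event.** Subjects who normalized are compared with a mixture of true non-normalizers and subjects whose ALT was never abnormal.
- **Coded by status at the visit.** Never-abnormal subjects join the normalizers, so the same confounding acts in the opposite direction.
- **Left blank.** A standard logistic fit drops them. Once HBeAg loss is in the model only HBeAg-positive subjects remain, so baseline HBeAg serostatus is constant and cannot be estimated.

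Table 4.20.3 could therefore present baseline ALT or HBeAg group as an on-treatment predictor of fibrosis improvement, with a sign set by an unstated programming choice. Alternatively, it could report a subset analysis under an mITT title.

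**Working it through.** **Plan's own figures.** The SAP gives no figure for this model, only the study size. N = 0.05 × 0.95 × (1.96/0.034)² = 157.8, so 158; 158/0.85 = 185.9, so 186. Both reproduce.

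**Assumed inputs.** The documents give no share at risk, event rate or improvement rate. Base case for ALT: 55% abnormal at baseline, 65% of these normalize, improvement 50% in the abnormal group and 25% or 35% in the normal group. Within each group, improvement is unrelated to normalization, so the true effect is nil.

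**Expected contrast, 50% versus 25%.**

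- Coded as no event: the event group improves in 50%. The other group is 0.55 × 0.35 = 0.1925 (true non-normalizers) plus 0.45 (never abnormal), total 0.6425. Its improvement rate is (0.1925 × 0.50 + 0.45 × 0.25)/0.6425 = 32.5%. The apparent odds ratio is (0.50/0.50)/(0.325/0.675) = 2.08. Never-abnormal subjects make up 0.45/0.6425 = 70% of the comparison group.
- Coded by visit status: the event group is 0.55 × 0.65 = 0.3575 plus 0.45, total 0.8075. It improves in (0.3575 × 0.50 + 0.45 × 0.25)/0.8075 = 36.1%, against 50% in the other group. The apparent odds ratio is (0.361/0.639)/1 = 0.56, so the sign reverses.

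**Rejection rates under no true effect.** Simulated 2×2 chi-square test, N = 186; ranges are over repeated runs of 1,500 to 4,000 trials.

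| Improvement, abnormal vs normal ALT | Coded no event, P ≤ 0.05 | Visit status, P ≤ 0.05 | At-risk only, P ≤ 0.05 | Coded no event, P ≤ 0.20 |
|---|---|---|---|---|
| 50% vs 25% | 64–65% | 33–35% | 4–5% | 84–86% |
| 50% vs 35% | 28–30% | 15% | 4–6% | 53–56% |
| 50% vs 50% | 5% | 5% | 5–6% | 20% |

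At N = 158 the first row is 58–59% coded as no event and 29–30% by visit status. A separate run with a logistic Wald test used N = 158, 40–70% abnormal, 50–70% normalizing and improvement 60% versus 40%. It gave 20–47% coded as no event and 9–25% by visit status.

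**HBeAg loss.** Assumptions: 40–60% HBeAg-positive, 8–15% loss by Week 24, improvement 60% in HBeAg-positive subjects, N = 186, chi-square test. Coded as no event, rejection is about 6–9% for a 15-point gap between the groups and 9–18% for a 25-point gap. Other runs over the same range reached about 20%. Few subjects lose HBeAg, so the no-event group changes little. Visit-status coding is worse: 46% at 50% positive, 10% loss and 60% versus 45% improvement. The Wald test at N = 158 gave 1–8% coded as no event and 26–35% by visit status.

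**Blank coding.** If both factors enter and the two traits are independent, the number kept is 186 × P(HBeAg-positive) × P(abnormal ALT):

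- 186 × 0.40 × 0.40 = 29.8
- 186 × 0.50 × 0.55 = 51.2
- 186 × 0.60 × 0.70 = 78.1

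**The case against.** The strongest reply is that the SAP states no wrong test. Read with the denominators in 5.2 and 7.4.2.3, subjects not at risk have no value, 6.2 does not impute, and each univariate test then runs in its at-risk subset at about 5%. The table shells are a separate document (SAP 9) and may settle the coding. That stands for the univariate tests. It does not rescue a multivariable model that loses the same subjects, nor the mITT label on its table.

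Second, baseline factors are already candidates. With baseline HBeAg serostatus in the model, HBeAg loss coded as no event is estimated within HBeAg-positive subjects. In a check at 40–50% positive, 10–15% loss and 15–25 point gaps, rejection fell from 5–17% to 2–3%, and serostatus passed the screen in 77–98% of trials. Baseline ALT value adjusts only in part: with a lognormal ALT assumed, multivariable rejection fell from 63% to 35% (50% versus 25%) and from 28% to 17% (50% versus 35%). So the univariate rates overstate what the multivariable model would report, but entry of these factors is not guaranteed.

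Third, no document gives improvement by baseline ALT. A reader might infer a difference from the LSM stage cut-offs in SAP 7.4.2.3, which are 27–36% lower for normal than for raised ALT (1 − 9.0/12.4 = 27%; 1 − 6.0/9.4 = 36%). But the outcome is a relative fall in LSM, and the cut-offs do not enter it. If raised ALT inflates stiffness, a fall on normalization would be a real effect of normalization. The size of the bias therefore rests on assumption.

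**Conclusion.** The point holds as a covariate and population left undefined in an mITT model, where either yes/no coding can confound the event with baseline group. Under the stated assumptions the ALT test at nominal 5% rejects in about 30–64% of trials coded as no event and 15–33% by visit status. With no baseline-group difference it stays near 5% under any coding. For HBeAg loss coded as no event the distortion is modest, up to about 20%, and baseline serostatus largely corrects it if it enters; visit-status coding distorts more.

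Three stronger readings are not supported:

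- That the test simply compares baseline groups. The contrast is a mixture of at-risk and not-at-risk subjects, and the coding is not stated.
- That no coding gives a valid test. Blank values leave the univariate tests valid.
- That most subjects are deleted. One blank factor removes only its own not-at-risk share. The loss to 30–78 of 186 needs both factors blank in one model, at the assumed 40–60% HBeAg-positive and 40–70% abnormal ALT. At 80% and 80%, 0.8 × 0.8 = 64% would remain.

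No formal hypothesis is tested in the study, this model is exploratory, and the primary endpoints are unaffected.

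**What to change.** In SAP 7.4.3:

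1. Run the univariate test and the P ≤ 0.20 screen for each of these factors only in its at-risk subset: abnormal baseline ALT for normalization, HBeAg-positive at baseline for HBeAg loss.
2. If a factor is selected, keep all mITT subjects in the multivariable model by coding the event 0 for subjects not at risk and forcing in the matching baseline indicator. In logit p = α + βA + γE, with A the at-risk indicator and E the event, γ is then the within-at-risk contrast. Use baseline HBeAg serostatus for HBeAg loss and baseline ALT abnormal (yes/no) for ALT, entered once to serve both Week 24 and Week 48.
3. Report only γ as the effect of the event, state whether the lab or the AASLD definition of ALT applies, and give n for each model.

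In the Wald simulation, adding the baseline group brought the ALT factor back to 3–6% at P ≤ 0.05 and 19–21% at P ≤ 0.20.

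A plain three-level factor is not enough. If its overall test drives the screen, it enters in 97–98% of trials (50% versus 25%) or 72% (50% versus 35%) with no true effect. The Week 24 and Week 48 ALT factors would also share a level, so one parameter would be aliased.

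The cost is a paragraph of SAP text and recoded covariates. Each contrast rests on fewer subjects, so its confidence interval is wider: at-risk shares of 40%, 50% and 70% leave 63, 79 and 111 of 158.

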#### **6.2.7. Liver fibrosis endpoint**

Liver fibrosis will be assessed using non-invasive FibroScan in all study subjects, and by formal liver biopsy in a subset of study subjects.

To assess liver fibrosis changes non-invasively a liver stiffness measure (LSM) will be obtained for all patients by transient elastography using FibroScan (EchoSens) at times outlined in Table 1.

. The LSM result will be expressed as a median value of the total measurements in kiloPascal (kPa). Only subject examinations with at least 10 validated measurements, a success rate of at least 60%, and an interquartile range (IQR) of all validated measurements of less than 30% will be considered a reliable LSM measure. Mean changes of LSM at Week 48, Week 96, Week 144, Week 192 and Week 240 will be reported.

To evaluate the proportion of subjects who experience an improvement in histology at Week 216 a subset of study subjects (approximately 100 subjects) will undergo liver biopsies at times outlined in Table 1.

A single central pathologist will evaluate all baseline and final biopsy slides in a paired fashion and blinded to timing of biopsy. The baseline and end of treatment biopsies will be read at the same time. (See Appendix 3)

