6. STATISTICAL CONSIDERATIONS

6.1 General rule

All analysis will be conducted using SAS® Version 9.2 or higher (SAS Institute, Cary, NC). For continuous variables, descriptive statistics will be presented as the mean, standard deviation, minimum, median, maximum, and the number of observations, unless otherwise specified. For categorical variables, the number and percentage for each of the categories will be presented. Counts that are zero will be displayed as “0”. Unless otherwise specified, the denominator for all percentages will be based on the number of subjects in the analysis set of that treatment group. Baseline is defined as the last assessment before administration of the study drug.

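### SAP 7.4.3 relates early LSM change, and baseline LSM itself, to a 30% LSM fall measured from the same single baseline reading, with no outcome visit named

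*SAP*

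**What the plan says.** All of this sits in SAP 7.4.3, Exploratory analysis, unless stated.

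- Outcome: "Improvement of fibrosis is defined as at least 30% decrease of LSM compared with baseline". This sentence belongs to the Cox model for time to improvement. The logistic model that follows uses the same outcome and names no visit for it.
- Logistic predictors include "baseline ALT value, baseline LSM value, baseline total bilirubin" and "change from baseline of LSM at Week 12 and Week 24". Age, sex and factors with univariate P of 0.20 or less enter the multivariate model.
- A separate analysis does name a visit: "Correlation coefficients between variables change at Week 12 and 24 and LSM change at Week 240 will be analyzed by correlation coefficients and P-value". LSM is one of the variables whose Week 12 and Week 24 changes are used.
- SAP 6.1: "Baseline is defined as the last assessment before administration of the study drug". SAP 6.2 adds, for the baseline value, "if it is missing at baseline visit, then the latest non-missing value of screening will be used to replace".
- Protocol 6.2.7: "a liver stiffness measure (LSM) will be obtained for all patients by transient elastography using FibroScan (EchoSens) at times outlined in Table 1". Table 1 ticks FibroScan at screening, at baseline and at every later visit. SAP 3.1 rules out study drug between screening and baseline.
- The HCC and progression models, logistic and Cox, include Week 24 and Week 48 response (HBV DNA below 20 IU/mL). In SAP 7.4.1 time runs from first dose, HCC counts from Week 24, and progression counts at any time before Week 240. No landmark is given. On missing values SAP 6.2 says: "In general, values for missing data will not be imputed unless otherwise specified".

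**The concern.** A baseline reading that is high by chance makes the Week 24 fall and the later fall both look large. A reading that is low by chance does the reverse. Early change then appears to foretell late improvement, and a high baseline LSM appears to favour improvement, even when neither carries information. With no outcome visit, a Week 12 or Week 24 reading could also be the reading that satisfies the outcome. The P of 0.20 entry rule would carry the artefact into the multivariate model.

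At stake is a reported finding that early LSM decline or high starting stiffness predicts fibrosis improvement. These are listed exploratory endpoints (SAP 5.3).

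The secondary concern is order in time. Progression can occur before either response is measured. HCC can precede the Week 48 response but not the Week 24 response, since HCC is counted only from Week 24. The HCC and progression models serve the third aim in Protocol 1.2.

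**Working it through.** **Plan's own figure.** None is given for these models. The sample size reproduces: 0.05 × 0.95 × (1.96/0.034)² = 157.9, so 158; 158/0.85 = 185.9, so 186.

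**Assumptions for LSM (not in the documents).** Log-scale reading error has SD s, and all subjects share the same average fall (22 to 30%). True early and late changes vary between subjects with SD τ and are unrelated. Protocol 6.2.7 gives one anchor. If the 30% IQR limit is relative to the median, single measurements have SD of at most 0.30/1.349 = 0.222. The median of 10 then has standard error 1.253 × 0.222/√10 = 0.09. That leaves out day-to-day variation, so I show s from 0.05 to 0.25.

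**Shared baseline, outcome at Week 240.** The two log changes share the baseline error, so their covariance is s² and each has variance 2s² + τ²:

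r = s²/(2s² + τ²), and approximately log OR per SD = 1.7 r/√(1 − r²).

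| s | τ | r | OR, approximation | OR, simulation |
|---|---|---|---|---|
| any | 0 | 0.50 | 2.7 | about 2.6 |
| 0.25 | 0.2 | 0.0625/0.165 = 0.38 | 2.0 | 1.9 |
| 0.10 | 0.2 | 0.01/0.06 = 0.17 | 1.3 | 1.3 |
| 0.09 | 0.2 | 0.0081/0.0562 = 0.14 | 1.3 | 1.3 |
| 0.05 | 0.2 | 0.0025/0.045 = 0.06 | 1.1 | 1.1 |

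The first row is the extreme case: no true difference between subjects. In that case adjusting for baseline LSM leaves an OR of 1.9 to 2.7, and baseline LSM alone has a null OR of 1.4 to 2.8 (s from 0.10 to 0.25).

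**Predictor from screening, outcome from baseline.** With screening and baseline errors correlated at ρ, the covariance becomes ρs², so r is ρ times its value above. In the extreme case:

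- ρ = 0: r = 0, OR 0.99 to 1.01.
- ρ = 0.3: r = 0.3 × 0.50 = 0.15, OR about 1.3.
- ρ = 0.6: r = 0.6 × 0.50 = 0.30, OR about 1.7.

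So 30% and 60% of r remain. On the log-odds scale, ln(1.66)/ln(2.72) = 51% to ln(1.69)/ln(2.57) = 56% remains at ρ = 0.6.

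**Scale.** In the logistic model with a screening-based predictor and ρ = 0, log and kPa both give a null OR of about 1.0. In the change-on-change correlation, kPa still gives null r of 0.06 to 0.47 with separate readings, because stiffer livers lose more kPa for the same percentage fall. The log ratio gives about 0.

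**Response timing.** Assume constant hazards, 10% progression and 15% dropout by Week 240, N = 186. With h = −ln 0.90 = 0.1054 and d = −ln 0.85 = 0.1625, expected progression events are 186 × 0.1054/0.2679 × (1 − 0.765) = 17.2. By Week 24 the count is 1.9 and by Week 48 it is 3.8, leaving 15.3 and 13.4. HCC at 5% over Weeks 24 to 240 gives 8.5 events, 7.5 of them after Week 48.

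- No imputation, response unaffected by the event: null HR 0.97 to 1.02.
- Case A, all early-event subjects stay and the event costs some of them their response. With 80% response and 25% of responders losing it, non-response among early events is 0.20 + 0.25 × 0.80 = 0.40. The early share is 3.8/17.2 = 0.22, so non-response among all events is 0.22 × 0.40 + 0.78 × 0.20 = 0.244. The ratio for non-response is (0.244/0.756)/(0.20/0.80) = 1.29. With 10% losing response it is 1.11; simulation gives 1.29 and 1.13.
- Case B, all early-event subjects leave before Week 48. A multivariable model holding Week 48 response then loses up to 3.8 of 17.2 progression events.

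A and B are alternatives and cannot both occur in full.

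**The case against.** The best defence is that these are exploratory analyses in a single-arm study without hypothesis tests, and that the SAP speaks of relationships and correlations. The reading error is unknown. The quality rules in Protocol 6.2.7 hold within-examination error to about 0.09, where the artefact is modest if true change varies. The descriptive table of the same 30% criterion is set at Weeks 48 to 240, so an outcome at any visit may never have been intended. This limits the size. It does not remove the shared reading, and the logistic model still names no visit.

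A reader might infer that moving to the screening reading removes the artefact, or most of it. The documents do not support that. The two readings are at most four weeks apart and untreated, and the SAP's LSM cut-offs depend on ALT, so a component common to both readings is plausible. Nothing in the documents shows the errors to be independent.

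A reader might also infer that the response hazard ratios are biased as planned. Under the no-imputation rule the null HR is about 1. Large distortion would require coding missing response as non-response, which the SAP does not call for. Nor do the documents settle how many early-event subjects have Week 48 HBV DNA. SAP 3.1 lets them withdraw or continue. Protocol 4.4 withdraws them yet keeps them eligible for drug and scheduled visits, and requires withdrawal after interruptions of 28 days or more. Table 1 footnote 3 places an evaluation in the 12 weeks after stopping drug.

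**Conclusion.** The shared-baseline defect is real and can be read directly from the SAP. Its size is conditional: r 0.50 and OR about 2.6 per SD in the extreme case; r about 0.17 to 0.38 and OR about 1.3 to 1.9 with true-change SD 0.2 and error SD 0.10 to 0.25; OR only about 1.1 to 1.3 at error SD 0.05 to 0.09. The Week 12 and 24 versus Week 240 LSM correlation has the same fault. The remedy is complete only with independent screening and baseline errors.

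The timing point is secondary. Bias arises only if subjects with an early event remain in follow-up and the event alters their response. If they leave instead, the cost is lost events.

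The analyses should be respecified because the change is cheap and uses scheduled data. No primary result is affected.

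**What to change.** **LSM.**

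- Where early LSM change is the predictor, set the outcome at Week 240.
- Compute the predictor change from the screening LSM and the outcome from the baseline LSM, in subjects who have both. Do not apply the screening-for-baseline replacement of SAP 6.2 here.
- Use the screening LSM as the starting-level covariate. Keeping baseline LSM in that place leaves a null OR of 1.04 to 1.15, because entry selects on the screening value.
- Treat the LSM term in the Week 12 and 24 versus Week 240 correlation the same way, with log ratios.
- Report the results with the caveat that about 30% of the spurious r remains at error correlation 0.3 and about 60% at 0.6.

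**Response.** Fit baseline factors from first dose with all events. Assess response in landmark models among subjects event-free and in follow-up, counting only later events, in the logistic versions too. Use Week 24 or Week 48 for progression. For HCC, assess Week 24 response from Week 24 and Week 48 response from Week 48. A model with both responses starts at Week 48.

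**Cost.** SAP wording and extra model runs; no new data.

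- The LSM analysis needs both pre-dose readings and a Week 240 reading. If a further 5 to 20% lack one (assumed), intervals widen by 3 to 12%, since √(1/0.95) = 1.03 and √(1/0.80) = 1.12.
- Power for a real association may be low: 20 to 92% at N = 150 with true early-late correlation 0.5 and true-change SD 0.2, depending on reading error.
- Landmark intervals for progression widen by √(17.2/15.3) = 1.06 at Week 24 and √(17.2/13.4) = 1.13 at Week 48. For HCC the factor is √(8.5/7.5), about 1.07, at Week 48; no counted event is lost at Week 24.
- Events before the landmark are not assessed for response.
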